9.2 Sample size justification

Seventeen patients are enrolled to evaluate the primary endpoint. A success rate of 60% of patients adequately debulking (defined as having low Tumor Burden at the end of cycle 0) will be considered compelling, establishing the feasibility of this approach, and support further studies. A success rate of 30% would be not compelling for further studies. With 17 patients, the study is adequately powered to evaluate this. A Simon's two-stage minimax design is utilized, with stopping for futility if an insufficient number of patients are debulked by HDMP/Rituximab. This design will have 80% power to reject the null hypothesis at 4% significance level and conclude that the true debulking rate at cycle 0 is above 30%, if the observed rate is ≥60%. Note that if patients are still meeting med/high tumor burden, they may repeat cycle 0 once more.

The null hypothesis that the true debulking rate is 30% at Cycle 0 will be tested against a one-side alternative. In the first stage, 10 patients will be accrued. The study enrollment will be put on hold for interim analysis until the response results for Stage 1 patients are known. If there are 2 or fewer responses (patients achieving low Tumor Burden) in these 10 patients, the study will be stopped. Otherwise, 7 additional patients will be accrual for a total of 20. The null hypothesis will be rejected if 9 or more responses are observed in 17 patients.

Early stopping probability: Under this design, if the null hypothesis is true, the probability of stopping the trial early will be 38.3%. The sample size calculation was done using PASS version 14.0.3 (released September 22, 2015). Sample size calculation did not incorporate the safety endpoint. Statistics for safety outcomes will be presented descriptively.

Accrual and study duration

We expect to accrue 1-2 patients every month. All patients will be accrued within 12-24 months. Patients will be followed for 24 months. The total duration of this study will be about 36 months.

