9.7	Statistical Analysis and Sample Size Justification	This is a pilot/feasibility clinical trial, with the primary feasibility endpoint being debulking of tumor burden to meet criteria for Low Tumor Burden upon the completion of cycle 0. Sample Size Justification: 17 patients are enrolled to evaluate the primary endpoint. A success rate of 60% of patients adequately debulking (defined as having Low Tumor Burden at the end of cycle 0) will be considered compelling, establishing the feasibility of this approach, and support further studies. A success rate of 30% would be not compelling for further studies. With 17 patients, the study is adequately powered to evaluate this. A Simon's two-stage minimax design is utilized, with stopping for futility if an insufficient number of patients are debulked by HDMP/Rituximab:

		The null hypothesis that the true debulking rate is 30% will be tested against a one-side alternative. In the first stage, 10 patients will be accrued. If there are 2 or fewer responses (patients achieving Low Tumor Burden) in these 10 patients, the study will be stopped. Otherwise, 7 additional patients will be accrual for a total of 17. The null hypothesis will be rejected if 9 or more responses are observed in 17 patients. This design yields a type I error rate of 0.04 and power of 80% when the true response rate is 60%. Under this design, if the null hypothesis is true, the probability of stopping the trial early will be 38.3%. The sample size calculation was done using PASS version 14.0.3 (released September 22, 2015).

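### Section 9.2 gives a total of 20 for 10 + 7 patients (it is 17) and ties the 80% power to an observed, not a true, rate of 60%

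*Combined protocol and SAP*

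**What the plan says.** Section 9.2 describes a Simon two-stage minimax design with a null debulking rate of 30% and a target of 60%. Stage 1 accrues 10 patients and the trial stops if 2 or fewer respond. The next step reads "Otherwise, 7 additional patients will be accrual for a total of 20".

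Elsewhere the same section gives 17 three times: "Seventeen patients are enrolled to evaluate the primary endpoint", "With 17 patients, the study is adequately powered to evaluate this" and "The null hypothesis will be rejected if 9 or more responses are observed in 17 patients". The synopsis (Table 1, row 9.7) has "17 patients are enrolled to evaluate the primary endpoint" and, in the sentence that parallels the one in 9.2, "Otherwise, 7 additional patients will be accrual for a total of 17".

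On power, Section 9.2 says that the design has 80% power at the 4% level to reject the null and "conclude that the true debulking rate at cycle 0 is above 30%, if the observed rate is ≥60" per cent. The synopsis says "This design yields a type I error rate of 0.04 and power of 80% when the true response rate is 60" per cent.

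**The concern.** Two statements in the section that defines the sample size are wrong.

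- **The total.** The stage sizes do not add up to the total given, so Section 9.2 contains two totals, 17 and 20. The rejection rule is defined only for 17. If anyone accrued to 20, the plan would not say how to count the three extra patients, and keeping the cut-off of 9 would raise the type I error.
- **The power condition.** Power is the probability of rejecting the null at an assumed true rate. Once the observed rate is known, the decision is known too, so a power of 80% given an observed rate has no meaning. The clause could also suggest that success needs 60% observed, which is not the rule.

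**Working it through.** **Inputs** (Section 9.2, with the same design values in the synopsis): null rate 0.30; alternative 0.60; stage 1 size 10; stop if 2 or fewer respond; stage 2 size 7; reject if 9 or more respond in total. Stated results: type I error 4%, power 80%, early stopping under the null 38.3%.

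**Step 1. The total.** 10 + 7 = 17.

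**Step 2. Reproduce the plan's figures with 17 patients.** Let X1 be the number of responses in stage 1 and X2 the number in stage 2.

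- Early stopping under the null: P(X1 ≤ 2 | 10, 0.3) = 0.7^10 + 10 × 0.3 × 0.7^9 + 45 × 0.3^2 × 0.7^8 = 0.0282 + 0.1211 + 0.2335 = 0.3828.
- Probability of rejection at true rate p: the sum over x = 3 to 10 of P(X1 = x | 10, p) × P(X2 ≥ 9 − x | 7, p).
- At p = 0.3 this is 0.0402. At p = 0.6 it is 0.8008.

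All three agree with the stated figures after rounding. A search for the minimax design, assuming limits of 5% for type I error and 80% for power, also returns 10 then 17 patients with the same two bounds.

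**Step 3. Try 20 patients.** Keep stage 1 as it is and let stage 2 have 10 patients. Early stopping stays at 0.3828, because it depends on stage 1 only, so that figure cannot separate 17 from 20. The other two can:

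| Total | Reject at | Type I error | Power at 0.60 |
|---|---|---|---|
| 17 | ≥ 9 | 0.0402 | 0.8008 |
| 20 | ≥ 9 | 0.1107 | 0.9391 |
| 20 | ≥ 10 | 0.0476 | 0.8706 |
| 20 | ≥ 11 | 0.0171 | 0.7548 |
| 20 | ≥ 12 | 0.0051 | 0.5955 |

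Both quantities fall as the cut-off rises, so no cut-off for 20 patients gives 4% and 80% together.

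**Step 4. The power clause.**

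- A trial stopped at stage 1 has at most 2/10 = 20% observed, so an observed rate of 60% or more can arise only with all 17 patients.
- 10/17 = 58.8% and 11/17 = 64.7%, so it means 11 or more responses.
- Stage 2 adds at most 7, so 11 responses need at least 11 − 7 = 4 in stage 1. The futility rule is therefore passed.
- Since 11 exceeds the bound of 9, P(reject | observed rate ≥ 60%) = 1, not 0.80.
- At a true rate of 60%, P(11 or more of 17) = 0.4478. The probability of rejection at that true rate is 0.8008. The two conditions are not interchangeable.
- The rejection bound is 9/17 = 52.9% observed. Results of 9 or 10 of 17 reject the null although they lie below 60%.

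**The case against.** The strongest reply is that no careful reader would be misled. The stage sizes are given, the sentence straight after the wrong total sets the rejection rule for 17, and the synopsis has both points right. On power, the same section names 60% as the rate of interest and speaks of a true debulking rate when it states the null. The decision rule does not rest on the power sentence, so no analyst would act on the literal reading. It can also be said that 20 patients with rejection at 10 or more would meet conventional limits of 5% and 80%.

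Much of this stands. The documents resolve both slips by themselves, and it limits the point to a minor correction. The power clause is the lesser of the two: its numbers are right and only its condition is wrong. The last remark is also true, but it describes a design that the plan does not state; the plan's own 4%, 80% and bound of 9 fit 17 only. What does not follow is that the text can be left alone. Section 9.2 is the main statement of the sample size, and it should give one total and a valid power statement.

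**Conclusion.** Both statements are wrong as written. The total should be 17, and the 80% power belongs to a true rate of 60%. The design as specified elsewhere is correct: 0.0402, 0.8008 and 0.3828 against the stated 4%, 80% and 38.3%. If 20 patients were enrolled and the cut-off of 9 kept, the type I error would be 0.1107; nothing in the documents shows that this is intended. The point is minor.

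The check assumes independent patients with a common response probability and covers the binomial arithmetic only. It does not address whether a response is counted after one cycle of debulking or after up to two.

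**What to change.** Make two replacements in Section 9.2, both in line with the synopsis:

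1. Change the total after stage 2 from 20 to 17.
2. State the 80% power as holding when the true debulking rate is 60%, in place of the condition on the observed rate.

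The cost is two edits to wording. Sample size, stopping bound, rejection bound, type I error and power are unchanged, and this point needs no further amendment.

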9.3 Analysis Populations

The Treated population will include all treated subjects who receive at least 1 dose of methylprednisone or rituximab.

9.4 Demographics and Baseline Characteristics

Subject baseline characteristics will be listed and summarized for the Treated population, including subject age, gender, prior therapy, IgVH mutational status, and molecular profiling including cytogenetics and mutation testing (if available).

9.5 Definition of Baseline Measurements

Baseline measurements will be the last measurement for the corresponding variable prior to the first study drug dose.

9.6 Study Drug Exposure, Concomitant Medications, and Nonprotocol Cancer therapy

Descriptive information will be provided regarding drug exposure: the number of cycles of HDMP + Rituximab, the number of months of venetoclax treatment, the number of prescribed dose modifications and interruptions; and the reasons for dose modifications and interruptions.

Concomitant medications will be listed and summarized as appropriate.

Subsequent non-protocol cancer therapy will be listed and summarized as appropriate, if available.

9.7 General considerations of statistical analyses

The statistical analysis of the data obtained for this study will be documented using summary tables and subject data listings. Continuous variables will be summarized using descriptive statistics, specifically the number of observations, mean, median, standard deviation, and minimum and maximum values. Categorical variables will be summarized by frequencies and percentages. For proportions, a 95% confidence interval will be calculated using the exact method. For survival outcomes, median survival times together with their 95% confidence intervals will be estimated with the Kaplan-Meier method, and report number of events.

All statistical tests will be two-sided at the 5% significance levels, unless otherwise noted.

9.7.1 Primary Efficacy Analyses

If applicable, "Intention-to-treat" analyses will be performed for the primary efficacy endpoint. To be specific, if the endpoint for a subject cannot be

assessed (for example, a subject drops out early prior to the tumor burden assessments due to any reason), it will be considered to be an event that does not favor the study therapy (e.g., disease progression for the primary outcome).

Primary efficacy analysis includes interim efficacy analysis and final efficacy analysis for the primary endpoint.

The interim efficacy analysis will be conducted at the end of Stage 1. The study enrollment will be put on hold for interim analysis until debulking response results for Stage 1 patients are known.

The final efficacy analysis will calculate the UMVUE estimate, p-value and 95% CI for the primary endpoint. ¹⁰⁻¹¹ The calculation will be performed using R *clinfun* package (www.r-project.org).

9.7.2 Secondary Analyses

Analysis for the secondary analyses will use the data combined from both the stages. Linear models, logistic models or Cox models will be used to adjust for covariates including the stage variable and whether a patient has a debulking response after the first cycle.

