		The combination of venetoclax and rituximab is an effective and FDA-approved regimen to treat patients with CLL or SLL who have previously received treatment. In a randomized phase 3 clinical trial, the 2-year PFS was 84.9% (bendamustine-rituximab comparator arm 2-year PFS was 36.3%); the ORR was 93.3% with a CR rate of 26.8% (Seymour et al, 2018).
		In part due to highly potent apoptosis induction, there is a known risk of tumor lysis syndrome (TLS) with venetoclax. This risk is mitigated by careful prophylactic and monitoring measures during the initiation of venetoclax, including inpatient hospitalization and serial lab monitoring for patients who have a high tumor burden. With such measures, the rate of grade 3 or 4 TLS was 3.1% in the venetoclax-rituxmab trial (Seymour et al, 2018). However, further TLS risk mitigation will improve outcomes with this treatment.
2.1	Rationale & Background Information	This risk of TLS is associated with the amount of tumor burden. Patients with Low Tumor Burden (absolute lymphocyte count less than 25k/uL; all lymph nodes less than 5 cm in diameter) are considered to have low TLS risk, and can be monitored without hospitalization (Venetoclax prescribing information). Therefore, decreasing the CLL tumor burden prior to initiation of venetoclax can also be a risk mitigation strategy.
		The combination of High-Dose Methylprednisolone (HDMP) and rituximab has been evaluated as a treatment for patients with CLL (Castro et al, 2008 and Castro et al, 2009). For patients with fludarabine-refractory CLL, the ORR was 96%, the CR rate was 36%, and all patients would have met the above criteria for Low Tumor Burden at the completion of therapy. Imaging was not done after just 1 cycle, so the precise degree of debulking at that time point is not known; however, the ALC values reduced in majority of patients within the 1st cycle.
		Therefore, HDMP + Rituximab is a potential debulking strategy prior to initiation of venetoclax based on the following rationale: - high rate of improvement of lymphadenopathy and lymphocytosis in previous publications lack of added myelotoxicity; and manageable overall toxicity profile compared to rituximab + venetoclax alone administration in an outpatient setting.
3.0	Core Protocol	
3.1	Study Objectives and Purpose	Purpose: to determine the feasibility of treating patients with HDMP + rituximab as a means of debulking prior to initiating venetoclax. Objectives:
		Primary:

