2.2.3.3 Summary of Clinical Efficacy of Venetoclax with Rituximab

The combination of venetoclax and rituximab was evaluated in a randomized, open-label, phase 3 trial. 389 patients were randomized to receive venetoclax for up to 2 years (from day 1 of cycle 1) plus rituximab for the first 6 months (venetoclax-rituximab group) or bendamustine plus rituximab for 6 months (bendamustine-rituximab group). The trial design did not include crossover. The primary end point was investigator-assessed progression-free survival.

The treatment regimen utilized the same dose escalation/ ramp-up strategy as utilized in early monotherapy trials. Rituximab was added on week 6, after completion of the ramp-up. Patients received rituximab 375 mg/m2 for the 1st dose, then 500 mg/m2 for 5 additional monthly doses.

After a median follow-up period of 23.8 months, the rate of investigator-assessed progression-free survival was significantly higher in the venetoclax-rituximab group (32 events of progression or death in 194 patients) than in the bendamustine-rituximab group (114 events in 195 patients); the 2-year rates of progression-free survival were 84.9% and 36.3%, respectively (hazard ratio for progression or death, 0.17; 95% confidence interval [CI], 0.11 to 0.25; P<0.001 by the stratified log-rank test). The benefit was maintained across all clinical and biologic subgroups, including the subgroup of patients with chromosome 17p deletion; the 2-year rate of progression-free survival among patients with chromosome 17p deletion was 81.5% in the venetoclax-rituximab group versus 27.8% in the bendamustine-rituximab group (hazard ratio, 0.13; 95% CI, 0.05 to 0.29), and the 2-year rate among those without chromosome 17p deletion was 85.9% versus

41.0% (hazard ratio, 0.19; 95% CI, 0.12 to 0.32). The benefit of venetoclax plus rituximab over bendamustine plus rituximab was confirmed by an independent review committee assessment of progression-free survival and other secondary efficacy end points.

The rate of grade 3 or 4 neutropenia was higher in the venetoclax-rituximab group than in the bendamustine-rituximab group, but the rates of grade 3 or 4 febrile neutropenia and infections or infestations were lower with venetoclax than with bendamustine. The rate of grade 3 or 4 tumor lysis syndrome in the venetoclax-rituximab group was 3.1% (6 of 194 patients). (8)

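### Section 9.7.2's two-covariate logistic model usually has no finite estimate for TLS and ORR at the documents' own rates, and for debulking after one cycle the covariate is the outcome

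*Combined protocol and SAP*

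**What the plan says.** Section 9.7.2 is the whole plan for the secondary analyses. It pools the data ("Analysis for the secondary analyses will use the data combined from both the stages") and then states that "Linear models, logistic models or Cox models will be used to adjust for covariates including the stage variable". The second covariate it names is cycle-1 debulking status. It assigns no model to any endpoint and gives no fallback for sparse data.

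The sample size comes from section 9.2: "In the first stage, 10 patients will be accrued", then 7 more, and "The null hypothesis will be rejected if 9 or more responses are observed in 17 patients".

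Section 9.1 lists the secondary endpoints: debulking after one cycle and after two cycles, laboratory TLS, clinical TLS, adverse events, ORR/PR/CR rates, and the undetectable MRD rate. Separately, section 9.7 provides a descriptive analysis: "For proportions, a 95% confidence interval will be calculated using the exact method".

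**The concern.** Logistic regression has a finite maximum-likelihood estimate only if events and non-events overlap across the covariate patterns. Seventeen patients spread over four stage-by-debulking cells give little room for that when an outcome is rare, as TLS is expected to be, or nearly universal, as ORR is. The stated analysis would then usually yield an infinite or non-convergent odds ratio, and the analyst would have to drop a covariate, penalise or change test after seeing the data.

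The cycle-1 debulking covariate raises two further problems. It is itself one of the secondary endpoints. It is also measured between Day 15 and Day 28 of Cycle 0 (section 6.2), whereas TLS is counted from the start of treatment, so TLS during the Cycle 0 infusions would be adjusted for something observed later.

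**Working it through.** **The plan's own figures.** Section 9.7.2 states none. The design figures reproduce. Stopping under the null: P(X ≤ 2 | 10, 0.30) = 0.0282 + 0.1211 + 0.2335 = 0.3828 (stated 38.3%). Summing over stage-1 counts of 3 to 10 with rejection at 9 or more of 17 gives type I error 0.0402 (stated 0.04) and power 0.8008 at 60% (stated 80%).

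**Inputs.** N = 17, stages 10 and 7 (section 9.2). TLS 3.1%, 6 of 194, grade 3 or 4 (section 2.2.3.3). ORR 93.3% and CR 26.8% (synopsis, rationale and background). Assumed, because the documents give no figure: TLS at 10% and 20%, undetectable MRD at 50%, and cycle-1 debulking of 40-80%.

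**A bound by hand.** With no event, or only one, the model is always separated.
- TLS at 3.1%: expected events 17 × 0.031 = 0.53. P(0) = 0.969^17 = 0.585; P(1) = 17 × 0.031 × 0.969^16 = 0.318. Sum 0.90.
- ORR at 93.3%: expected non-responders 17 × 0.067 = 1.14. P(0) = 0.933^17 = 0.308; P(1) = 17 × 0.067 × 0.933^16 = 0.376. Sum 0.68.

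**Full probability.** The model is intercept + stage + cycle-1 debulking, with the outcome independent of both covariates. Each of the four cells is empty, all 0, all 1 or mixed. A linear program classes each pattern as having a finite estimate or not (separated or rank-deficient), and exact binomial probabilities are summed over the patterns.

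| Outcome | Rate | P(no finite estimate), debulking 40-80% |
|---|---|---|
| TLS | 3.1% (grade 3 or 4) | 0.97-0.98 |
| TLS | 10% (assumed) | 0.78-0.87 |
| TLS | 20% (assumed) | 0.44-0.65 |
| ORR | 93.3% | 0.88-0.94 |
| CR | 26.8% | 0.27-0.52 |
| Undetectable MRD | 50% (assumed) | 0.07-0.34 |

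The minimum falls at a debulking rate near 50%. Simulation with 100,000 trials at 60% debulking gave 0.972 for TLS and 0.890 for ORR, against 0.972 and 0.888 by enumeration.

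**Sensitivity.**
- Requiring at least 3 of 10 debulked in stage 1 changes the TLS (3.1%) and ORR results by about 0.01 or less.
- An assumed 15% not evaluable raises ORR to 0.92-0.93 (debulking 60% and 30%).
- Section 9.2 also gives a total of 20, although 10 + 7 = 17. With 10 + 10 the results are 0.96-0.97 for TLS and 0.85-0.87 for ORR (same debulking rates).
- The probability drops below 0.90 once the event rate exceeds about 6.3-6.6%.

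**Debulking endpoints.** For debulking after one cycle, outcome and covariate are identical, so the model is separated at any rate. For debulking after two cycles, section 4.2 limits the assessment to patients not yet low after cycle 1; in that subset the covariate is constant and has no estimable coefficient.

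**Linear and Cox models.** Every secondary endpoint in section 9.1 is a proportion or an event frequency. None is continuous or time-to-event.

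**The case against.** Five points can be made for the plan.

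1. The 3.1% is for a different event. The endpoints are laboratory and clinical TLS without a grade limit, and laboratory TLS needs only two metabolic abnormalities (Appendix B), in patients enrolled for Medium or High tumor burden. This stands. A reader might infer that the model fails in nine of ten trials for any TLS endpoint; the documents support that only at the grade 3 or 4 rate.

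2. A reader might infer that two-covariate regression is impossible for every secondary endpoint. It is not. At the rates used, a finite fit exists in about 48-73% of trials for CR and 66-93% for MRD. The problem there is imprecision.

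3. A reader might infer that linear and Cox models could have no use at all. Section 9.6 describes quantitative exposure variables, section 6.7 records dates of progression or next therapy where available, and section 9.7 mentions survival outcomes. What stands is narrower: no endpoint in 9.1 needs these models and no time-to-event endpoint is defined.

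4. Section 9.7 already supplies exact intervals and section 9.2 makes safety descriptive. This stands, so the defect is confined to the adjusted models. The term logistic model would also allow a penalised version, but 9.7.2 does not name one.

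5. The go/no-go decision uses only the primary two-stage rule. This also stands, and it limits the consequence.

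**Conclusion.** The concern holds for TLS and ORR at the documents' rates, and with certainty for debulking after one cycle. The logistic model in 9.7.2 has no finite estimate in about 97-98% of trials for TLS at 3.1% and 88-94% for ORR at 93.3%. This assumes 17 evaluable patients, outcomes independent of the covariates and cycle-1 debulking of 40-80%. If laboratory TLS were as common as 20%, failure would still occur in 44-65% of trials. For CR and MRD the model often fits but would be too imprecise to be more than exploratory. The TLS model also adjusts Cycle 0 events for a later measurement.

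This is a stated method that usually cannot be carried out for TLS and ORR at those rates, so the section should be corrected. The primary analysis and the exact intervals are sound.

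**What to change.** Reword section 9.7.2 as follows:
- Make counts with exact 95% confidence intervals, already in 9.7, the stated analysis for all binary secondary endpoints.
- Also cross-tabulate TLS, ORR, PR, CR and MRD by cycle-1 debulking status; for TLS, include only events after the Cycle 0 reassessment.
- Drop the cycle-1 debulking covariate for the debulking endpoints.
- For TLS and ORR, replace the two-covariate logistic model with Fisher's exact test or a one-covariate Firth logistic model, labelled exploratory.
- Label any adjusted model kept for CR, PR or MRD as exploratory.
- Remove the linear and Cox models unless an endpoint that needs them is defined.

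The cost is a change of wording and somewhat less analysis; no new data or patients are needed. What is lost is adjusted odds ratios for TLS and ORR, which could usually not be estimated at the documents' rates.
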